7.2. Study Setting

Inclusion and exclusion criteria:

- a) Patients with a histologically confirmed diagnosis of advanced renal cell carcinoma without prior therapy and at least 3 of 6 prognostic risk factors or relapsed/refractory mantle cell lymphoma for whom a decision was already made to treat with temsirolimus.
- b) Patients with histologically confirmed diagnosis of advanced/metastatic renal cell carcinoma or unresectable and/or metastatic GIST, after imatinib failure, for whom a decision was already made to treat with sunitinib.
- c) Patients with histologically confirmed diagnosis of advanced renal cell carcinoma after failure of prior therapy with sunitinib or a cytokine for whom a decision was already made to treat with axitinib.
- d) Written informed consent form from the patient is obtained prior to enrollment into the registry.

Due to the non-interventional nature of the registry, no specific requirements apply regarding the management of treatment. Dosing and duration of treatment will be decided by the physician according to individual treatment requirements of the patient.

Extract from the Summary of Product Characteristics

During the treatment of patients with temsirolimus, sunitinib, and axitinib, among other things, the section "Contraindications" of the respective Summary of Product Characteristics must be taken into account. In case of hypersensitivity reactions, the advice in the relevant Summary of Product Characteristics must be observed.

[figure not shown]
- a) In particular, the following excerpts are included under Section 4 "Clinical particulars" of the Summary of Product Characteristics of temsirolimus:
 - Hypersensitivity to the active substance or to any of the excipients of temsirolimus
 - It is recommended that patients be given an H1 antihistamine before an infusion of temsirolimus. In case of known hypersensitivity to antihistamines or in patients who cannot receive an antihistamine for another medical reason, temsirolimus should be used with caution.
 - Concomitant use of substances that affect CYP3A metabolism: CYP3A4 inducers: e.g. dexamethasone, carbamazepine, phenytoin, phenobarbital, rifabutin, rifampicin, St John's wort
 - CYP3A4 inhibitory agents: e.g. atazanavir, clarithromycin, indinavir, itraconazole, ketoconazole, nefazodone, nelfinavir, ritonavir, saquinavir, telithromyzine.
 - Concomitant use of sunitinib
 - Vaccinations
 - Pregnancy.

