The biometric evaluation of the patient data (including statistical analysis plan) takes place, appropriate to the design of a registry, in a purely descriptive manner, and will be performed by a Contract Research Organization (Winicker Norimed GmbH, Nuremberg). An annual interim analysis will be performed.

Definition of analysis set

All prospectively documented patients with a histologically confirmed diagnosis of renal cell carcinoma, MCL, and GIST will be included in the "safety population".

All patients to whom at least one of the following criteria apply will be included in the "efficacy population": Date of death, time of progression, physician's assessment of therapy response, or therapy assessment of efficacy and tolerability by the physician are available.

Retrospectively documented information will not be included in the analysis.

Analysis of Safety Criteria

The absolute and relative frequency of patients with adverse events will be shown in a tabular form, both globally and according to the system organ classes and the MedDRA "preferred terms". In addition, the absolute and relative frequency of therapy dropouts will be presented both overall and according to discontinuation reasons. Serious adverse events will be evaluated separately. Previous and concomitant therapies will also be tabulated.

Laboratory analysis and electrocardiogram results will be analyzed per visit. In addition, the physician will assess information on tolerability during therapy.

Analysis of Efficacy Criteria

The change in disease activity will be described using the following parameters:

[figure not shown]
- Assessment of response to therapy by the physician
- Physician's assessment of efficacy
- Overall survival (OS)
- Progression-free survival (PFS)
- Maximum Response

For the analysis in STAR-TOR, the duration of treatment is defined as the period between inclusion in the registry and occurrence of any of the events of either death or discontinuation of the documentation or termination of therapy.

The duration of treatment will be evaluated using methods from the field of "survival time analysis".

Other analysis parameters

Comorbidities will be coded in accordance with MedDRA and concomitant medications according to WHO-DD. Frequencies for appropriate coding levels will be presented. Evaluation of sequence and therapy regimens and quality of life (advanced RCC) will be performed.

Case number estimate

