[figure not shown]
With Amendment VII, the additional documentation period defined in Amendment VI is reduced by one year. As of September 15, 2020, 17 patients were registered in an interim documentation. Of these, 2 patients received follow-up therapy with axitinib. It is shown that the approval of three new ICI combinations which are all prominently represented in guidelines has reduced recruitment for sunitinib patients in first-line therapy (prerequisites for later use of axitinib) and/or has been moved to later lines of therapy. Documentation of 45 patients in the stated time does not seem possible at this recruitment rate to answer the question of Amendment VI. Therefore, the further recruitment phase is reduced by one year (to the end of December 2020).

Discussion of potential bias sources

In this non-interventional registry, the selection of documented patients is not subject to a randomization mechanism, so that a selection bias cannot be excluded.

A comparison of the safety and efficacy of temsirolimus, sunitinib, and axitinib is planned. Potential confounders will be considered and will be included in the statistical analysis plan accordingly. Subgroup analyses, e.g. patients stratified by concomitant diseases, age, and gender, may be performed in addition, if appropriate.

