5 ANALYSIS SETS/POPULATIONS

Analyses will be performed within each indication and treatment, e.g. one for mRCC and temsirolimus, sunitinib and axitinib, one for the non-Pfizer interim therapies and one for MCL and one for GIST.

For data from mRCC patients included prior to amendment VI of the protocol baseline data from sequence 1 will be forwarded as baseline data for sequence 2, if the respective data is not asked for in follow-up 1 of sequence 2 (tumor anamnesis at time of primary diagnosis, prior local and systemic therapies, prior and concomitant diseases, concomitant medication (other than systemic therapy)). Ongoing adverse events from sequence 1 have to be added to the list of concomitant diseases in sequence 2. Additional cancer therapy from baseline and follow-up visits of sequence 1 will be forwarded as baseline data for sequence 2 unless the therapy has been discontinued.

For patients included under amendment VI, baseline data for the second Pfizer treatment will be asked for in the CRF as changes in this data are not completely asked for in the non-Pfizer treatment periods.

For data from mRCC patients the following tables (see chapter 9): demographic information (1.2-1; 1.2-2), study periods (1.1-5.2), previous local and systemic therapy (1.5-1; 1.5-2), duration of therapy (1.6-1), overall survival (2.2-1), progression free survival (2.3-1), course of Karnofsky performance scale (2.5) and course of FKSI-15 (2.6), EQ-5D (2.7) will be repeated for the following groups of patients:

- Treatment sequence 1^{st} sunitinib $\rightarrow 2^{nd}$ axitinib \rightarrow any further therapy
- Treatment sequence 1^{st} temsirolimus $\rightarrow 2^{nd}$ sunitinib \rightarrow any further therapy
- Treatment sequence 1^{st} sunitinib \rightarrow any further therapy (no axitinib in 2^{nd} line)
- Treatment sequence 1^{st} temsirolimus \rightarrow any further therapy
- Treatment sequence 1^{st} sunitinib \rightarrow no further therapy
- Treatment sequence 1^{st} temsirolimus \rightarrow no further therapy
- Any therapy $\rightarrow 2^{\text{nd}}$ axitinib \rightarrow any further therapy.

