8.1.2 Analysis Of Survival Data

OS, PFS and treatment duration will be analyzed using Kaplan-Meier plots. Median, 25% and 75% survival times with confidence intervals for OS and PFS will be presented. For stratification according to physician's prognosis and for risk groups according to Motzer score/MIPI/Fletcher risk table, log-rank tests will be performed.

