1.3-1.4	Tumor anamnesis - other information	GIST	SAFETY, EAS	.1 Frequency table for size of primary tumor, sample statistics for number of mitoses, frequency table for primary mutation analysis performed?, frequency table for type of KIT-mutation .2 Frequency table for mutation analysis performed in recidive?, frequency table for type of mutation
CCI				
1.3-3	ECG	mRCC, GIST	SAFETY, EAS	Frequency tables for normal/abnormal ECG by time window

Table No.	Title	Treatment/ Indication	Analysis set	Description
CCI				

Table No.	Title	Treatment/ Indication	Analysis set	Description
CCI				
				, number of transplantations, R0 resection reached

Table No.	Title	Treatment/ Indication	Analysis set	Description
CCI				

Table No.	Title	Treatment/ Indication	Analysis set	Description
CCI				
2	Effectiveness			
2.1	Response to therapy			
2.1-1	Course of response to therapy	All	EAS	Frequency table by time window (in total and by patient risk groups)

Table No.	Title	Treatment/ Indication	Analysis set	Description
2.1-2	Best response	All	EAS	Frequency table for best response in total and confirmed / not-confirmed (the latter not for Torisel® MCL); Frequency table for best response excluding patients "not assessable" only for MCL Listing of reasons for not assessable best response; Frequency table for best response by patient risk groups
2.1-3	Used diagnosis technique	All	EAS	CT, Thorax X-ray, MRT, Ultrasonic testing, PET, Bone scan, Clinical (by time window and for best response)
2.2	Overall survival			
2.2-1	Kaplan-Meier estimates for Overall survival	All	EAS Sequence analysis	Time to 25%, median and 75% survival with confidence intervals incl Kaplan-Meier curve on all patients
2.2-2	Kaplan-Meier estimates for Overall survival by patient risk groups	mRCC	EAS	 .1 Physicians prognosis of patients risk .2 Risk groups according to Motzer score .3 Risk groups according to modified Motzer score .4 Risk groups according to Motzer score for pretreated patients .5 by treatment sequence .6 by treatment and treatment line. .7 1st line patients by risk (poor vs. non-poor) .8 by LDH ≤ 300 U/l vs > 300 U/l incl. Log-ranktest and Kaplan-Meier curves

Table No.	Title	Treatment/ Indication	Analysis set	Description

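### The protocol plans a three-drug comparison with confounders handled in the SAP, but the SAP specifies no adjusted or risk-stratified drug contrast, and its mRCC overall-survival display by drug and line mixes drug with eligibility-driven risk

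*Protocol*

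**What the plan says.** **Protocol, section 11.** Under biometric evaluation, the analysis is to be done "in a purely descriptive manner". The discussion of bias sources concedes that selection bias cannot be excluded, and then states: "A comparison of the safety and efficacy of temsirolimus, sunitinib, and axitinib is planned". The next sentence is "Potential confounders will be considered and will be included in the statistical analysis plan accordingly". No method is named.

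**Protocol, section 7.2.** Temsirolimus patients with renal cell carcinoma must be "without prior therapy and at least 3 of 6 prognostic risk factors". Sunitinib patients with renal cell carcinoma face no risk criterion. Axitinib patients are enrolled "after failure of prior therapy with sunitinib or a cytokine for whom a decision was already made to treat with axitinib".

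**SAP.**
- Section 5: "Analyses will be performed within each indication and treatment".
- Section 6.4 (Covariates) uses prognostic scores to group patients, not as terms in a model.
- Section 8.1.2 says that "log-rank tests will be performed", but the full sentence refers to strata of physician's prognosis and of the risk scores. It does not refer to drugs.
- Section 9, Table 2.2-2 (mRCC, overall survival) lists item "6 by treatment and treatment line". The same cell ends by calling for a log-rank test and Kaplan-Meier curves.
- Section 8.2.2 shows adverse events within each treatment.
- Sections 4.1 and 4.2 (hypotheses, decision rules) are marked not applicable.

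**The concern.** The protocol passes the handling of confounders to the SAP, and the SAP does not take it up for any contrast between drugs. It has no Cox or other regression, no propensity method and no drug test stratified by risk. The blacked-out SAP tables do not explain this, because the survival methods and the effectiveness tables are legible.

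The overall-survival display by drug and line is therefore the natural place to look for the planned comparison, and it is confounded by eligibility. Splitting by line does not help. Within first line, temsirolimus is restricted to patients with several adverse prognostic factors and sunitinib is not. If a log-rank p-value is attached to that display and carried into a conference abstract or the final paper (protocol section 12.1), nothing in the plan tells the reader how much of the difference comes from patient selection.

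**Working it through.** **1. Is there a figure to reproduce?** No. The documents give no hypothesis, effect size, event count or alpha for a drug comparison, so the size below rests on assumptions.

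**2. Where can the drugs overlap?** From the renal cell carcinoma criteria in protocol section 7.2:

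| Drug | Line | Risk restriction |
|---|---|---|
| Temsirolimus | untreated only | at least 3 of 6 factors |
| Sunitinib | any | none |
| Axitinib | pretreated only | none stated |

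Temsirolimus and sunitinib overlap in first line among poor-risk patients. Sunitinib and axitinib overlap in later lines. Temsirolimus and axitinib share no line.

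**3. Is a matching stratifier available?** Yes. SAP section 6.4.1 defines the modified Motzer score as five factors plus one, with three or more counted as poor, for first-line patients only. This is the same count threshold as the temsirolimus criterion. However, Table 2.2-2 lists treatment by line (item .6) and first-line patients by risk (item .7) as separate displays.

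**4. Size with no true drug effect.** Let *p* be the poor-risk share on sunitinib and *h* the hazard ratio of poor to non-poor risk, and take all first-line temsirolimus patients as poor risk. The apparent hazard ratio at time zero is then

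HR₀ = h / (p·h + 1 − p).

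For p = 0.35 and h = 2: 2 / (0.70 + 0.65) = 2 / 1.35 = 1.48. The ratio drifts upward during follow-up, because poor-risk patients die earlier and leave the sunitinib group.

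A simulation adds follow-up. Its assumptions, none from the documents, are exponential survival, non-poor median 24 months, censoring uniform from 6 to 72 months, and 1,000 runs per scenario with a two-sided 0.05 test. At 200 patients per drug:

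| p | h | HR₀ | Crude HR | Crude rejection | Stratified HR | Stratified rejection |
|---|---|---|---|---|---|---|
| 0.20 | 1.5 | 1.36 | 1.38 | 75% | 0.98 | 5.9% |
| 0.20 | 2 | 1.67 | 1.76 | 100% | 0.98 | 6.3% |
| 0.20 | 3 | 2.14 | 2.50 | 100% | 0.99 | 5.3% |
| 0.35 | 1.5 | 1.28 | 1.30 | 58% | 0.99 | 5.6% |
| 0.35 | 2 | 1.48 | 1.59 | 98% | 0.99 | 4.4% |
| 0.35 | 3 | 1.76 | 2.10 | 100% | 0.99 | 4.7% |
| 0.50 | 1.5 | 1.20 | 1.22 | 39% | 0.99 | 5.5% |
| 0.50 | 2 | 1.33 | 1.43 | 87% | 0.99 | 6.3% |
| 0.50 | 3 | 1.50 | 1.77 | 100% | 1.00 | 5.8% |

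Over 100, 200 and 400 patients per drug, the crude hazard ratio is 1.22–2.50 with rejection in 24–100% of runs. Stratified by risk it is 0.96–1.00, with rejection in 3.8–6.5%.

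These hazard ratios are one-step log-rank estimates, exp(U/V), which run high when the ratio is large. A Cox fit to one sample of 8,000 per drug gave about 2.3 in the p = 0.20, h = 3 cell and 1.21 in the p = 0.50, h = 1.5 cell. The top of the range is better read as 2.3 to 2.5.

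**5. Sensitivity to the temsirolimus assumption.** SAP section 5.4 singles out first-line temsirolimus patients with poor modified Motzer prognosis, so some may not be classed as poor. With a poor-risk share *q* on temsirolimus, HR₀ = (q·h + 1 − q) / (p·h + 1 − p). For an assumed q = 0.8, p = 0.35 and h = 2: 1.8 / 1.35 = 1.33 instead of 1.48. The bias shrinks but does not vanish.

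**The case against.** The strongest defence is that this is a descriptive registry. The evaluation is declared descriptive, there are no hypotheses or decision rules, and the protocol itself warns of selection bias. The SAP also uses the prognostic factors. Section 5.4 repeats mRCC effectiveness analyses by physician's prognosis and three Motzer scores. Section 8.2.3 lists risk, line, LDH, response to prior therapy and age as strata for survival. Since tables are by default repeated per treatment and indication, first-line poor-risk survival for temsirolimus and for sunitinib can be set side by side. All of this stands. It narrows the gap to one missing item: a between-drug estimate within comparable patients.

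A reader might infer four stronger things that the documents do not support:
- **That the SAP offers only crude log-rank tests.** It has the risk-group analyses just listed.
- **That drugs are log-rank tested for progression-free survival as well.** The mRCC log-rank curves under Table 2.3-2 are by line, age, LDH and histology, and none is by drug.
- **That a between-drug test is beyond doubt.** The sentence in section 8.1.2 concerns risk groups. In Table 2.2-2 the log-rank note follows item .8, and it may cover the whole list or only part of it.
- **That the protocol promised an adjusted model, or that the sponsor intends to read the result as a drug effect.** The protocol says only that confounders will be considered and included. Misreading is a foreseeable risk, not a stated aim.

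The descriptive label does not remove the point. The protocol also says that a comparison is planned, and a log-rank p-value by drug would be an inferential statement.

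**Conclusion.** The point holds in a limited form. The protocol's planned three-drug comparison, with confounders to be covered in the SAP, has no counterpart there: no adjusted or risk-stratified drug contrast is specified for efficacy or safety. The mRCC overall-survival display by drug and line mixes drug with eligibility-driven risk, and splitting by line does not separate them.

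Under the assumed inputs and no drug effect, the crude hazard ratio against temsirolimus is about 1.2 to 2.5, and about 1.0 once stratified by risk. The direction follows from the criteria, provided that the risk factors are prognostic. The size depends on the assumed poor-risk share and prognostic strength, so it cannot be said from the documents that selection accounts for most of any observed difference. A single Cox model across all three drugs would not repair this. Temsirolimus and axitinib share no line under the criteria, so that contrast would rest on extrapolation through sunitinib.

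**What to change.** 1. **Table 2.2-2, item .6:** remove the between-drug log-rank p-value, keep the crude Kaplan-Meier curves as description, and state which items the log-rank note covers.
2. **Any between-drug statement on overall survival (and on progression-free survival, if one is made):** limit it to drug pairs that overlap in line and risk, chiefly first-line temsirolimus versus sunitinib in modified-Motzer poor-risk patients. Use a Cox model adjusted for the Motzer factors (Karnofsky status, LDH, hemoglobin, corrected calcium, time from diagnosis), metastatic sites, histology and age. Report the hazard ratio with 95% CI.
3. **Dependence:** where a contrast lets one patient contribute two drug sequences, account for it, for example with patient-clustered standard errors.
4. **Missing covariates:** state the rule. SAP section 7 covers assignment to risk groups but not a regression model.
5. **Scope:** state that temsirolimus and axitinib are not compared because they share no line of therapy, and that the safety tables by drug are descriptive. Reconcile the comparison sentence in protocol section 11 with this.

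The cost is SAP wording and a few models on data already collected. Some patients will lack covariates, and the restricted contrast covers fewer patients and will be less precise.

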12. COMMUNICATION AND PUBLICATION OF RESULTS

12.1. Publication Plan

It is planned to perform annual interim analyses and present their results as an abstract at the appropriate national and international specialist conferences. Formal interim reports are not planned. It is planned to publish the final study results in a peer-reviewed journal.

The final CSR is planned for 2022.

12.2. Communication of safety problems

In case of any enacted prohibition or restriction (e.g. suspension of the study) by a competent authority, or if the treating physician becomes aware of any new information that might affect the benefit/risk assessment of a Pfizer product, Pfizer should be informed immediately.

In addition, the treating physician will notify Pfizer immediately of any actions he has taken to protect the study patients from immediate harm to health. He also will inform Pfizer of any serious violations of the observational plan of this non-interventional study of which he is aware.

1 AMENDMENTS FROM PREVIOUS VERSION(S)

Amendment from version 1.0

In the course of the NIS for patients with metastasized renal cell carcinoma treated with Torisel[®], regarded treatment and regarded indication was extended. In the NIS are currently included patients with metastasized renal cell carcinoma treated with either Torisel[®] or Sutent[®], patients with mantle cell lymphoma treated with Torisel[®] and patients with gastrointestinal stroma tumors treated with Sutent[®].

For this reason the statistical analysis plan had to be amended from version 1.0.

Amendment from version 2.0

In the course of the NIS for patients with metastasized renal cell carcinoma treated with Torisel[®], was further extended regarding treatment. Patients suffering from metastasized renal cell carcinoma being treated with Inlyta[®] are now also included in the NIS. Furthermore the documentation of two patient questionnaires (Functional Assessment of Cancer Therapy - Kidney Index - 15 (FKSI-15) and EuroQoL-5D (EQ-5D)) was added

for patients suffering from metastasized renal cell carcinoma.

Also the importance of the sequence of systemic treatments was strengthened leading to

Also the importance of the sequence of systemic treatments was strengthened leading to a new version of the case report form.

For these reasons the statistical analysis plan had to be amended from version 2.0.

Amendment from version 3.0

In the course of the NIS, the flow chart had to be updated as a starting visit for the 2nd therapy for mRCC patients was included.

Amendment in version 6.0

In the course of the NIS the following changes were implemented:

Rules for determination of therapy lines were added.

Additional plausible ranges for laboratory values were defined and actions after detections of not plausible ranges were defined.

Due to the possibility of documentation of treatment sequences, the determination of modified Motzer score was not possible without any doubt for the second treatment within a sequence. It was clarified, that modified Motzer score was determined only for 1st line patients.

The analysis on comorbidities was further specified, in order to combine data on comorbidities from old and new versions of the CRF.

Determination of time to progression and overall survival was further specified.

Amendment in version 7.0

In the course of the NIS, further specifications to determine therapy line for MCL subjects were added.

Amendment in version 7.1

In the course of the NIS, further analyses for specific subgroup were defined.

Amendment in version 7.2

In the course of the study, contents of already defined tables were further specified.

Amendment in version 8.0

In the course of the study, changes in study conduct due to amendment VI, dated Oct, 30th, 2017 had to be made.

Additionally SAP was transferred to the current Non-Interventional Statistical Analysis Plan template.

Amendment in version 9.0

In the ocurse of the study, it was recognized that the additional analyses defined in amendment VI would not be possible due to low recruitment. Thus study aims and duration of recruitment were changed. This led to necessary adoptions in this SAP.

